5.6.1.3.2. Vital Signs

All vital signs data as of the data cutoff date will be included.

Absolute values and changes from Baseline in vital signs (systolic and diastolic blood pressure, heart rate, respiratory rate, and temperature) will be summarized descriptively at each visit and treatment group. A listing of vital signs will be presented.

The number and percentage of participants with at least 1 post-treatment vital sign measurement meeting any of the following criteria will be summarized by treatment group:

- Systolic blood pressure: < 90, > 140, and > 160 mmHg
- Diastolic blood pressure: < 50, > 90, and > 100 mmHg
- Heart rate: < 60 and > 100 bpm
- Body weight: decrease of \geq 7% from Baseline and increase of \geq 7% from Baseline
- Temperature: $> 38.0^{\circ}$ C and $< 36.0^{\circ}$ C
- Respiratory rate: < 12 and > 20 breaths/min

This analysis will be performed for the PEP data only using the SS and separately for the aggregated PEP, ETP, and OLE Period (if applicable) data during the ALXN2050 treatment period using the ALXN2050-Treated Set.

Adverse changes from Baseline in physical examination findings will be classified as AEs and analyzed accordingly.

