- 10. Evidence of hepatitis B (hepatitis B positive hepatitis surface antigen [HbsAg] or positive hepatitis B core antibody [anti-HBc]) with negative surface antibody [anti-HBs] or hepatitis C viral infection (hepatitis C virus [HCV] antibody positive, except for patients with documented successful treatment and documented sustained virologic response [SVR]) at Screening.
- 11. History of malignancy within 5 years of the Screening Visit, with the exception of nonmelanoma skin cancer or carcinoma in situ of the cervix that has been treated with no evidence of recurrence.
- 12. History of persistent or recurrent infections prior to the Screening Visit.
- 13. Active systemic bacterial, viral, or fungal infection within 14 days prior to study intervention administration on Day 1.
- 14. Presence of fever as documented by a temperature  $\geq 38^{\circ}$ C (100.4°F) within 7 days prior to administration of study intervention on Day 1.
- 15. History or presence of any risk factors for Torsades de Pointes (eg, heart failure/cardiomyopathy or family history of Long QT Syndrome), a screening QT interval corrected using Fridericia's formula (QTcF) > 450 msec for males and > 470 msec for females, or receiving medications known to significantly increase the corrected QT interval (QTc).
- 16. Laboratory abnormalities at the Screening Visit, including:
  - a. Alanine aminotransferase  $> 2 \times$  the upper limit of normal (ULN)

- b. Direct bilirubin  $> 2 \times ULN$
- 17. Estimated glomerular filtration rate (eGFR) < 30 mL/min/1.73 m^2 and/or are on dialysis.
- 18. Any other clinically significant laboratory abnormality that, in the opinion of the Investigator, would make the participant inappropriate for the study or put the participant at undue risk.

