5.6.1.3.3. Electrocardiograms

Descriptive statistics by visit and treatment group will be presented for each ECG parameter (including PR, QRS, QT, corrected QT interval [QTc], and QTc using Fridericia's formula [QTcF]) value and for change from baseline values.

An outlier analysis that will summarize the frequency and percentage of participants who meet any of the following outlier criteria will be performed:

- QT and QTcF interval > 450 msec
- QT and QTcF interval > 480 msec
- QT and QTcF interval > 500 msec
- QT and QTcF interval increases from Baseline > 30 msec
- QT and QTcF interval increases from Baseline > 60 msec

This outlier analysis will be performed for the PEP data only using the SS and separately for the aggregated PEP, ETP, and OLE Period (if applicable) data during the ALXN2050 treatment period using the ALXN2050-Treated Set.

Overall ECG results will also be classified as normal, abnormal not clinically significant, and abnormal clinically significant. A summary table will be provided for clinically significant abnormalities by visit and treatment group.

A by-participant listing of ECG results will be presented.

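### The fixed-threshold vital-sign and ECG rows take no account of baseline, so the uncontrolled ALXN2050-period table cannot separate pre-existing from new abnormality

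*SAP*

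**What the plan says.** **Vital signs (SAP 5.6.1.3.2).** The counting rule is "The number and percentage of participants with at least 1 post-treatment vital sign measurement meeting any of the following criteria will be summarized". The limits for blood pressure, heart rate, temperature and respiratory rate are fixed, for example "Systolic blood pressure: < 90, > 140, and > 160 mmHg". Body weight is the exception: it is a change of at least 7% from baseline. The section also plans by-visit summaries ("Absolute values and changes from Baseline in vital signs") and a listing.

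**ECG (SAP 5.6.1.3.3).** The rule is "An outlier analysis that will summarize the frequency and percentage of participants who meet any of the following outlier criteria will be performed". Three rows are absolute limits for both sexes, starting with "QT and QTcF interval > 450 msec" and going on to 480 and 500 msec. Two rows are relative to baseline: "QT and QTcF interval increases from Baseline > 30 msec" and the same for 60 msec. By-visit changes, a table of clinically significant abnormalities and a listing are also planned.

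**Where the tables are used.** Each is produced for the PEP on the Safety Set, with placebo, and separately for the aggregated ALXN2050 treatment period on the ALXN2050-Treated Set, without concurrent placebo. Section 1.2 of the SAP addendum keeps all safety analyses.

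**Entry limits (Protocol 5.2).** Exclusion 15 bars a screening QTcF "> 450 msec for males and > 470 msec for females". Exclusion 14 bars a temperature of 38°C or more in the 7 days before Day 1 dosing. There is no numeric entry limit for blood pressure, heart rate, respiratory rate, low temperature or uncorrected QT.

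**Baseline for Groups 3a and 3b.** SAP 5.1.2 and 5.6.2 use the PEP baseline, before placebo, for non-efficacy data.

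**The concern.** A row that counts anyone with a post-dose value beyond a fixed limit mixes two kinds of participant: those who crossed the limit during the period and those who were already beyond it. Only the first kind says anything about change on treatment. A woman enrolled with a QTcF of 455 msec who stays there is counted above 450 msec. A participant whose systolic pressure is 150 mmHg throughout is counted above 140 mmHg.

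In the PEP table randomization balances pre-existing abnormality in expectation, so its main effect is to inflate the counts and dilute new events. In the ALXN2050-period table there is no such protection, and the row itself gives the reader no way to tell the two kinds apart.

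The SAP deals with this elsewhere. Laboratory values get shift tables (5.6.1.3.1), the C-SSRS gets a shift from baseline (5.6.1.3.4), and a TEAE must have started or worsened after first dose (5.6.1.2). The vital-sign and ECG limits have no equivalent.

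The ECG wording has a further gap. Protocol Table 2 schedules ECGs at Screening, Day 1, Week 8 and early discontinuation. For a PEP completer, Week 8 is the only scheduled ECG after Day 1. Without the word post-baseline, a Day 1 value could be programmed into the PEP outlier count.

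**Working it through.** The plan states no figure on this point, so there is nothing to reproduce. The text settles which rows are exposed; the size rests on assumptions.

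**Step 1. Which rows are exposed.**

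| Row | Baseline handled? |
|---|---|
| Systolic and diastolic pressure, heart rate, respiratory rate, temperature below 36.0°C | No, and no entry limit |
| Temperature above 38.0°C | No, but exclusion 14 makes it unlikely at baseline |
| QT above 450, 480, 500 msec | No, and no entry limit on uncorrected QT |
| QTcF above 450 msec | No; women may enter at 451 to 470 msec |
| QTcF above 480, 500 msec | No, but exclusion 15 makes it rare at baseline |
| QT and QTcF increases above 30, 60 msec; weight change of 7% | Yes |

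**Step 2. Range for a generic fixed limit.** Assumptions: no drug effect, one baseline and 8 weekly post-baseline readings (the PEP vital-sign schedule), normal values, within-participant correlation 0.5 or 0.7, and baseline prevalence q beyond the limit. Arm size is 70 × 2/5 = 28. Simulation of 200,000 participants per setting, with each range spanning the two correlations:

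| q | Flagged per 28 | Flagged who were beyond the limit at baseline | New onset among those not beyond it |
|---|---|---|---|
| 5% | 4.7–6.1 | 16–24% | 13–19% |
| 10% | 8.0–10.3 | 22–30% | 22–32% |
| 20% | 13.2–16.1 | 31–39% | 36–49% |
| 30% | 17.1–20.1 | 39–47% | 47–62% |

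**Step 3. One worked row, systolic pressure above 140 mmHg.** Assumptions: mean 128, between-person SD 14, visit SD 9, 8 visits, no drug effect. Simulated: 0.521 flagged, 0.235 above 140 at baseline, 0.392 flagged among the 0.765 not above it. The share of flagged participants already above the limit is (0.521 − 0.392 × 0.765) / 0.521 = 0.42.

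**Step 4. QTcF in women.** The share starting between 450 and 470 msec is [Φ((470 − μ)/18) − Φ((450 − μ)/18)] / Φ((470 − μ)/18), with an assumed SD of 18 msec. For μ = 420, 425 and 430 this gives 4.5%, 7.7% and 12.2%. That is the share at risk of being flagged without change, not the share flagged, because some would read 450 msec or below at Week 8.

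**Step 5. Chance imbalance in the PEP.** Two arms of 28 with the same baseline prevalence differ by 3 or more baseline-abnormal participants with probability 0.26, 0.40 and 0.47 for q = 10%, 20% and 30% (binomial).

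**Step 6. Would replacing the rows by new-onset counts be better?** Take the Step 3 row and the between-arm difference with no drug effect.
- As written: SD = √(2 × 0.521 × 0.479 / 28) = 13.4 percentage points.
- New onset only: expected denominator 28 × 0.765 = 21.4, and SD = √(2 × 0.392 × 0.608 / 21.4) = 14.9 points.

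Replacement therefore makes the between-arm comparison slightly noisier.

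**The case against.** A reader might infer that the SAP reports pre-existing abnormality as an on-treatment or drug-related finding. The documents do not support that. The SAP calls the counts post-treatment measurements and outliers, never treatment-emergent, and a post-dose pressure of 150 mmHg is correctly counted as a post-dose value above 140. Appearing in both the PEP and the ALXN2050-period table is not an error either, since these are two separately stated displays.

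Much of the information is available elsewhere. The weight row and the 30 and 60 msec rows already use baseline, by-visit changes and listings are planned, and clinically significant findings are to be recorded as adverse events (Protocol 8.2.3 and 10.3.1). The table specifications sit in a separate data presentation plan that is not available here, so the shells may show baseline counts. Safety is descriptive with no testing, and the trial was stopped for lack of efficacy with an abbreviated report. All of this stands and limits the severity.

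The case against simply replacing the rows also stands. Beyond Step 6, 39% of baseline-normal participants are flagged in the Step 3 model with no drug effect, through repeated noisy readings. That rises to 45% with 12 visits and about half with 18. Calling those treatment-emergent would invite over-reading.

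The objection does not remove the gap. By-visit means do not show who crossed a limit, the listings leave the reader to sort it out by hand, and the SAP text provides no threshold display by baseline status.

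**Conclusion.** The point holds in a narrow form and is minor. The affected rows are mainly systolic and diastolic pressure, heart rate, respiratory rate, low temperature, uncorrected QT, and QTcF above 450 msec in women admitted at 451 to 470 msec. In these rows new and pre-existing abnormality are mixed, and no stated shift table separates them. The consequence is greatest in the aggregated ALXN2050-Treated Set table. In the PEP, the randomized comparison remains valid in expectation, though chance imbalance between arms of 28 is quite possible.

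The absence of a baseline condition is a matter of text and is certain, as far as the SAP goes. The size is not: 16% to 47% of flagged participants already abnormal at baseline follows from assumed prevalences of 5% to 30% and correlations of 0.5 to 0.7, none of which the documents give. No efficacy inference and no stated decision rule depends on these rows.

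**What to change.** 1. In SAP 5.6.1.3.3, state that only post-baseline ECGs enter the outlier counts.
2. In 5.6.1.3.2 and 5.6.1.3.3, keep the existing any-post-baseline counts. Also present each fixed-threshold row by baseline status: new onset among participants not meeting the criterion at baseline, with that denominator, beside those who already met it. A baseline-by-worst-post-baseline shift table would serve equally well. Leave the change-from-baseline rows as they are.
3. For Groups 3a and 3b in the ALXN2050-period table, base this split on the last value before the first ALXN2050 dose, or show it beside the PEP baseline. Otherwise an abnormality that arose on placebo would count as new on ALXN2050. Vital signs and an ECG are already scheduled at Week 8, and the ETP starts only after that visit's assessments and before ALXN2050 is given.

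The cost is one extra display and a derivation flag, with no new data. New-onset denominators are smaller: about a quarter fewer for systolic pressure above 140 mmHg under the Step 3 assumptions, or roughly 7 of 28. A footnote should say that new-onset counts still include chance crossings from repeated readings and should not be read as drug-caused.

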b Neurologist or appropriately qualified other study team member as delegated by the Investigator, eg, senior neurology resident in training, physician assistant, or nurse practitioner. Vital capacity, which is part of the QMG assessment, may also be measured by a qualified physical therapist.

Abbreviations: C-SSRS = Columbia-Suicide Severity Rating Scale; gMG – generalized myasthenia gravis; MG-ADL = Myasthenia Gravis Activities of Daily Living; MGFA = Myasthenia Gravis Foundation of America; MGFA-PIS = Myasthenia Gravis Foundation of America Post-Intervention Status; Neuro-QoL™ Fatigue = Neurological Quality of Life Fatigue questionnaire; QMG = Quantitative Myasthenia Gravis score for disease severity There will be 4 periods in this study (Figure 1):

- Screening Period of up to 4 weeks During this timeframe, participants will present to the clinic at least once wherein screening procedures and assessments as indicated in the Schedule of Activities (SoA; Section 1.3 [Table 2]) will be performed to determine eligibility. The participant may be asked to return to the clinic for additional follow-up (eg, blood redraw), although it is not anticipated that this will be a frequent occurrence.
- Primary Evaluation Period of 8 weeks (Day 1 to Week 8) Treatment during this timeframe will be blinded for participants, Investigators, site personnel, and Alexion clinical study staff. The participant will present to the clinic every week for the first 8 weeks for fulfillment of procedures and assessments as specified in the SoA (Table 2). For the first visit on Day 1, and after confirmation of eligibility, the participant will be randomized to 1 of 3 treatment groups. The participant will be provided with sufficient study intervention to last until their next study visit. In the clinic, the participant will be administered a dose of study intervention (3 tablets). The participant will be instructed to take the second dose of study intervention (3 tablets) at home. The participant will also be dispensed the safety card that discusses some of the risks associated with treatment, and steps to take in the event of an emergency. The participant must be instructed to carry the safety card at all times. The last visit for the PEP will be the Week 8 Visit.

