- Extended Treatment Period of 26 weeks (Week 8 to Week 34) The ETP begins at the Day 57 (Week 8) Visit after all assessments of the visit are performed, but before the administration of ALXN2050 in the clinic and postdose PK/PD sampling. During this timeframe, participants in the ALXN2050 180 mg bid and ALXN2050 120 mg bid groups will continue taking the dose to which they are randomized. Participants in the placebo group will be stratified by MG-ADL total score at baseline (pre-placebo) and re-randomized in a 1:1 ratio to either ALXN2050 180 mg bid (Group 3a) or ALXN2050 120 mg bid (Group 3b). All participants will receive active study intervention; however, the actual dosage of ALXN2050 will be blinded to participants, Investigators, and site personnel. Visits at Weeks 9, 10, 11, 13, 14, and 15 will be conducted via telephone contact (Table 3). Participants will present for in-clinic visits at Weeks 12, 16, 26, and 34. The first dose of study intervention during in-clinic visit days will be administered by the site personnel. The participant will take the second dose of study intervention at home. The last visit for the ETP will be the Week 34 Visit.
- Open-label Extension Period of up to approximately 1.5 years (Week 34 to Week 117) – The OLE Period begins at the Day 239 (Week 34) Visit after all assessments of the visit are performed, but before the administration of ALXN2050 in the clinic and postdose pharmacokinetics/pharmacodynamics (PK/PD) sampling. During this timeframe, all participants will receive active study intervention. If an optimal dose of ALXN2050 has been identified, all participants will be switched to this optimal dose, as long they have completed the first 34 weeks of treatment. However, the actual dose of ALXN2050 will continue to be blinded to participants, Investigators, and site personnel during this study period until they are switched to the

optimal dose, if one is identified during the study. Participants will return to the clinic approximately every 3 months as indicated in the SoA (Table 4). The first dose of study intervention during in-clinic visit days will be administered by the site personnel. The participant will take the second dose of study intervention at home. The last visit for the OLE Period is the EOS Visit.

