5.6.1. Safety Analyses at Analysis 1 (Week 8)

All outputs for safety outcomes of the Primary Treatment Period (first 8 weeks) will be based on the SS, unless otherwise specified. All safety analyses for participants during the ALXN2050 treatment period will be based on the ALXN2050-Treated Set. Safety data will be summarized

by the actual treatment received (Groups 1, 2, 3, 3a, and 3b, as applicable). Baseline is defined as the last available assessment prior to the first dose of study intervention.

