1.2. Changes From Analyses Specified in the Previous Version of the SAP

- Primary endpoint: primary endpoint analyses will be performed as described in the SAP Amendment Version 1.0 Section 5.3.2. Sensitivity and supplementary analyses will not be performed.
- Secondary efficacy endpoints: only change from baseline in the QMG total score and change from baseline in the MG-ADL total score as described in the SAP Amendment Version 1.0 Section 5.4.1.1 and Section 5.4.1.3 (excluding the trend analysis to detect dose-response trend) will be performed. Descriptive summary of absolute and change from Primary Evaluation Period (PEP) baseline in MG-ADL and QMG total score will tabulate study visits through the entire study. Supplementary analyses will not be performed.
- PK/PD: PK parameter will not be reported as described in the SAP Amendment Version 1.0 Section 5.7.1.3. Population PK and exposure-response analysis will not be performed as described in the SAP Amendment Version 1.0 Section 5.7.3. All other PK/PD analyses will be performed.
- Biomarker: biomarker analysis will not be performed.
- Safety: All safety analyses will be performed as planned, as described in the SAP Amendment Version 1.0 Section 5.6 with all data collected until the end of study.
- No exploratory endpoint analyses will be performed.
- All other analyses (e.g., demographic, baseline disease characteristics, MG/non-MG medications/therapies, protocol deviation, etc), if not mentioned above, will be performed as planned.

Study exposure and adverse event data summaries will include the following two sets of analyses: (1) summary of the PEP data by Group 1, 2, 3; (2) summary of the ALXN2050 Treated Period data by Group 1, 2, 3a, 3b. Per-protocol Set and Re-randomized Set will be removed.

Medication summaries by treatment group and overall using the number and percentage of participants will be presented by WHO-DRUG Anatomical Therapeutic Chemical Level 3 class code and by WHO-DRUG generic name.

All planned listings other than the ones for exploratory biomarker endpoints will be produced.

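### In the ALXN2050-period vital-sign outlier table, the share of participants ever out of range is not comparable between Groups 1/2 and 3a/3b, because scheduled on-drug measurements to Week 34 are 12 versus 4

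*SAP*

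**What the plan says.** SAP 5.6.1.3.2 counts participants on an ever-out-of-range basis: "participants with at least 1 post-treatment vital sign measurement meeting any of the following criteria will be summarized by treatment group". The criteria cover blood pressure, heart rate, body weight, temperature and respiratory rate. The table is produced once for the PEP on the Safety Set, and then "separately for the aggregated PEP, ETP, and OLE Period (if applicable) data during the ALXN2050 treatment period using the ALXN2050-Treated Set". SAP 5.6.1 presents safety data "by the actual treatment received (Groups 1, 2, 3, 3a, and 3b, as applicable", so the re-randomized placebo participants appear as their own columns.

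SAP 5.6.1.3.3 uses the same two-table arrangement for ECG outliers. SAP 5.6.2.3 repeats these analyses on the first 34 weeks. Section 1.2 of the SAP addendum retains them: "All safety analyses will be performed as planned", with data collected to the end of the study.

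On the visit schedule, protocol 4.1 says of the PEP that "The participant will present to the clinic every week for the first 8 weeks", and of the ETP that "Participants will present for in-clinic visits at Weeks 12, 16, 26, and 34". The remaining ETP contacts are telephone calls, and Table 3 marks no vital signs for them.

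Neither outlier table adjusts for the number of measurements. By contrast, SAP 5.6.1.2 adds a rate per 100 patient-years for adverse events in the same ALXN2050 period.

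**The concern.** A participant enters the numerator on the first qualifying value, so the percentage depends on how often people are measured as well as on how often values are abnormal. Groups 1 and 2 are on ALXN2050 during the dense part of the schedule. Groups 3a and 3b spend that part on placebo and begin ALXN2050 as the schedule becomes sparse.

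Group 1 and Group 3a receive the same dose, as do Groups 2 and 3b, so a reader will naturally compare them. Fewer abnormalities in 3a/3b could then be read as better tolerability or as an effect of starting later, when some or all of the difference comes from visit counts.

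**Working it through.** The documents state no expected figure for this table, so there is none to reproduce. The check counts visits and then asks what the table would show if ALXN2050 had no effect.

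**Inputs from the documents**
- Vital signs after Day 1 in the PEP: Weeks 1 to 8, which is 8 (protocol Table 2).
- ETP: Weeks 12, 16, 26 and 34, which is 4 (Table 3).
- OLE: Weeks 52, 65, 78, 91, 104 and 117, which is 6 (Table 4).
- On dosing days vital signs precede the dose (Table 2 footnote). Day 1 is therefore pre-drug for Groups 1/2.
- The ETP starts after the Week 8 assessments and before the first ETP dose (Table 3 footnote). Week 8 is therefore pre-ALXN2050 for Groups 3a/3b.

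**On-drug scheduled counts**
- To Week 34: Groups 1/2 have 8 + 4 = 12; Groups 3a/3b have 4.
- To Week 117: 12 + 6 = 18 versus 4 + 6 = 10.
- ECG to Week 34: Weeks 8, 26 and 34 (3) versus Weeks 26 and 34 (2). The first in Groups 3a/3b comes after 26 − 8 = 18 weeks on drug.

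**Assumptions, because the documents give neither.** The same chance p that any one measurement is out of range applies in every group, and values within a participant have correlation ICC.

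**Formulae**
- Independent visits: P(ever) = 1 − (1 − p)^k, where k is the number of measurements.
- Correlated visits (beta-binomial): with s = (1 − ICC)/ICC, a = p·s and b = (1 − p)·s, P(ever) = 1 − product over j = 0 to k − 1 of (b + j)/(a + b + j).

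For p = 5% and independence: 1 − 0.95^12 = 46.0% and 1 − 0.95^4 = 18.5%. For ICC 0.5, s = 1, a = 0.05 and b = 0.95. With k = 4 this gives 1 − 0.95 × 0.975 × 0.9833 × 0.9875 = 10.1%.

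**Expected % ever out of range to Week 34, Groups 1/2 versus 3a/3b, no drug effect**

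| p | Independent | ICC 0.3 | ICC 0.5 | ICC 0.7 | ICC 0.9 |
|---|---|---|---|---|---|
| 1% | 11.4 v 3.9 | 4.6 v 2.7 | 3.1 v 2.1 | 2.1 v 1.6 | 1.3 v 1.2 |
| 5% | 46.0 v 18.5 | 21.2 v 12.7 | 14.5 v 10.1 | 10.0 v 7.8 | 6.5 v 5.9 |
| 10% | 71.8 v 34.4 | 38.2 v 24.3 | 27.3 v 19.4 | 19.3 v 15.3 | 12.8 v 11.7 |

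To Week 117 at p = 5%: 60.3% versus 40.1% if independent, 16.2% versus 13.8% at ICC 0.5, and 6.7% versus 6.4% at ICC 0.9.

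ECG to Week 34 at p = 5%, independent: 1 − 0.95^3 = 14.3% versus 1 − 0.95^2 = 9.8%.

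**Would a simpler adjustment do?** Dividing by patient-time would not, because visit density also differs: 12/34 = 0.35 per week versus 4/26 = 0.15 per week. Cutting both at 26 weeks on drug leaves 11 versus 4. The percentage of measurements out of range has expectation p in every group, whatever k is.

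**The case against.** The strongest reply is that this is a descriptive table. SAP 5.6 plans no hypothesis test on safety data, and protocol section 9 treats all results as exploratory. By-visit summaries and listings are planned, and no section sets out to compare Groups 1/2 with 3a/3b formally. That limits the consequence to a misreading. It does not make the percentages comparable, and the by-visit vital-sign summaries give values and changes rather than outlier percentages.

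The size is also open to challenge. Most criteria are fixed cut-offs. Someone whose systolic pressure usually exceeds 140 mmHg will be counted at any visit density, so correlation is likely and the independent case is near the upper end. At ICC 0.5 and p = 5% the gap is 14.5 − 10.1 = 4.4 points. With about 14 participants in each of 3a and 3b (half of the 28 planned on placebo), that is 0.044 × 14 = 0.6 of a participant. This stands: the documents do not support a prediction that the table will show far fewer abnormal participants in 3a/3b.

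Two stronger inferences are tempting, and the documents support neither:
- **That the active groups will look worse than placebo.** The placebo comparison sits in the separate PEP table, where Groups 1, 2 and 3 each have 8 scheduled measurements. A distortion arises only if someone reads a placebo figure from one table against an active figure from the other.
- **That the table is tilted against 180 mg.** No dose-pooled table of ALXN2050-period vital-sign outliers is planned. Summaries by dose are specified for adverse events and for OLE data by visit, and the OLE schedule is the same for everyone. As displayed, Group 1 versus 2 is 12 versus 12, and 3a versus 3b is 4 versus 4.

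Finally, restricting the table to matched visits would discard 8 of the 12 vital-sign measurements in Groups 1/2 to Week 34, and real outliers with them. That objection also stands, and it determines the form of the fix.

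**Conclusion.** The point holds for one comparison: Groups 1/2 against Groups 3a/3b in the ALXN2050-period outlier tables. Under no drug effect the expected percentage is always higher in Groups 1/2, and the gap closes only if a participant's values are perfectly correlated. Its size is uncertain because p and ICC are assumed. At 5% per measurement it runs from 46.0% versus 18.5% (independent) to 6.5% versus 5.9% (ICC 0.9). The ECG table has the same structure with a smaller imbalance.

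Limits on the counts:
- The 12 versus 4 does not apply to body weight, which is scheduled at Screening and otherwise belongs to the complete physical examination (protocol 8.2.1).
- Respiratory rate is listed in protocol 8.2.2 but not in the schedule's vital-sign footnotes, so its actual count should be checked.
- After early termination, follow-up varies by participant. Deterioration, early-discontinuation and unscheduled visits can add values. Actual counts will therefore differ from those scheduled, but stopping early does not remove the imbalance: a common stop at Week 16 would give 10 versus 2.

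This is a reporting weakness in a descriptive table that is cheap to correct. It does not affect the placebo comparison or the comparison between doses within each pair of groups.

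**What to change.** In the SAP addendum and table shells, for the ALXN2050-period vital-sign and ECG outlier tables:

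1. Keep the full participant-level count, so that no safety outlier leaves the table.
2. For each criterion and group, add the number of on-drug measurements and the percentage of those measurements out of range.
3. Add a footnote that the participant-level percentages are not comparable between Groups 1/2 and Groups 3a/3b, because the numbers of on-drug measurements differ.
4. Optionally, for vital signs, add a supplementary row restricted to visits matched on time since first ALXN2050 dose: Weeks 4, 8, 16 and 26 in Groups 1/2, and Weeks 12, 16, 26 and 34 in Groups 3a/3b. Subtracting 8 weeks for 3a/3b gives 4, 8, 18 and 26 weeks on drug against 4, 8, 16 and 26, so there are four measurements on each side.

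Measurements cluster within participants, and one person with persistent values can dominate a percentage of measurements. It should therefore stand beside the participant count and not replace it.

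The cost is a little more programming and a longer table. No new data are needed.
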